## RECRUITMENT AND ANALYSIS OF NON-PARTICIPANTS

Patients were recruited at the emergency department at Danderyd Hospital. Consecutive patients, seeking care for mTBI or a minor orthopedic injury were asked to participate in the study.

Subject recruitment was conducted between January 2015 and January 2016 and was stopped when a total of 15 patients with mTBI and 15 orthopedic controls were enrolled, in accordance with the power calculation.

Among the 129 patients who were asked for participation in the study (32 mTBI; 97 OC), a total of 99 people declined, 17 mTBI and 82 OC. Of those who declined, 88% of mTBI and 64% of orthopedic subjects were men, and there was no difference regarding age between participating and non-participating individuals. The reasons stated for not participating were lack of time and inconvenience. Two individuals in the mTBI group and two individuals in the orthopedic control group were lost to follow-up despite several follow-up phone calls and letters.

## DATA COLLECTION AND MANAGEMENT

A prospective controlled, observational fMRI-study, with assessments on average 7 days after injury (span 2-12 days) and 122 days after injury (span 81-324 days).

Study patients were contacted by phone 1–3 days after injury. All study participants received written information about the study and gave informed consent. All data related to the injury, GCS on arrival at the emergency department and results of CT of the brain were collected from the medical records. Demographic data were collected by interview at the baseline examination. All study participants were scheduled to be assessed two times: at baseline, in the subacute phase (for patients with trauma, 7–10 days after the trauma) and at follow-up 75–100 days after the injury. Due to recruitment difficulties and in order to minimize drop-out, the time frame for the first and second assessments was extended. The median time between injury and baseline visual assessment was 7 days (range 4–13 days) for patients with mTBI and was 8 days (range 7–12 days) for orthopedic controls. The median time between injury and follow-up visual assessment was 103 days (range 81–232 days)

for patients with mTBI and 109 days (range 87–322) for orthopedic controls. No statistically significant difference was found between patients with mTBI and the orthopedic control group regarding time between the injury and assessments (baseline and follow-up). Patients with mTBI and orthopedic controls underwent examination with structural MRI and resting state functional MRI of the brain at baseline and at follow-up.

#### *MRI DATA ACQUISITION PROTOCOL.*

The MRI data acquisition was conducted on a whole-body 3T clinical MRI scanner (Philips Ingenia, Philips Healthcare, Best, Netherlands) equipped with a 20-channel phased-array receiving head coil. All data was acquired at Danderyd University Hospital, Stockholm, Sweden. The MRI data acquisition protocol included the following scanning sessions: (1) 3-plane localizer; (2) Conventional clinical MRI scans including 3D T1-weighted TFE, 2D FLAIR, T2-weighted FFE, T2-weighted TSE and DWI with 32 direction; (3) resting-state fMRI FE-EPI 8 min. The main acquisition parameters included the following: TE/TR 35/3000 ms, flip angle= 90°, 32 slices of 4 mm thickness, FOV= 230mm, matrix size= 96 × 96, data acquisition acceleration with SENSE parallel imaging method (acceleration 1.8), and 160 dynamic timeframes. Each participant's head was carefully fixed in the head coil to reduce involuntary head motions. During the resting-state fMRI scans the participants were instructed to focus their sight on a white cross onto a black background projected on a screen installed in front of them. The participants were also instructed to not think about anything specific during the resting-state fMRI scans.

#### **MEASURES**

##### *SELF-ASSESSMENT*

For assessment of self-rated symptoms The Rivermead PostConcussion Symptoms Questionnaire (RPQ, (15)) was used. RPQ is based on a Likert scale and includes 16 items with ratings from 0 to 4. A score of 1 means that the symptom has been present but is no longer a problem and a score between 2 and 4 indicates symptom severity from 'mild to severe.'

Self-rated trait fatigability were rated with the Fatigue Severity Scale (FSS, (16)). FSS consists of 9 questions and is based on a 7 point Likert scale A high score implies a higher level of fatigue. It is one of the most frequently

used inventories for measuring fatigue in people with chronic illnesses and is considered to have robust psychometric properties (20).

Occurrence of depression and anxiety were screened with Hospital Anxiety and Depression Scale (HADS, (17)). The scale comprises of two separate scales for anxiety and depression. Scores range from 0 to 21, with scores from 0 to 7 representing a “normal,” 8–10 a “mild,” 11–14 a “moderate,” and 15–21 a “severe” level of anxiety or depression. The HADS has been widely used to assess anxiety and depression following TBI (21).

Self-rated near work related visual symptoms were measured with Convergence Insufficiency Symptom Survey (CISS, (18)). The CISS is a validated and reliable instrument which assesses both direct symptoms (eg. blurred vision, double vision) and indirect symptoms (eg. difficulty maintaining concentration, headache)(18). The survey includes 15 questions with ratings from 0 “never” to 4 “always”. Total score is 60 and the cut-off score for abnormally high levels of symptoms is 21.

Visual disturbances were measured by a licensed optometrist, using standard optometric methods. Included in the assessment was tests of visual acuity, refractive error, stereoacuity, accommodation, heterophoria, eye motility and fusional vergence. Diagnosis of visual dysfunctions were based on established diagnostic criteria (19).

Diagnosis of visual dysfunction was based on established diagnostic criteria. Visual functions were measured by a licensed optometrist, including assessment of refractive error, visual acuity, stereoacuity, heterophoria, fusional vergence, eye motility, near point of accommodation, and near point of convergence. A questionnaire, Convergence Insufficiency Symptom Survey (CISS), assessed visual strain during near work. Only convergence, accommodation, fusional vergence, and CISS will be analyzed in this project based on previous findings from the same dataset (22) and clinical experience.

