## AIM/OBJECTIVES

To investigate whether change in connectivity over time after mTBI, according to fMRI, varies depending on cognitive reserve compared to orthopedic controls and how this is related to symptoms and symptom resolution.

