## OUTCOME VARIABLES

Table 1: Outcome measures

Outcome measure	Measures
Primary outcome measures	
State fatigability	Difference between score during the first 60 and the last 60 seconds of the Digit Symbol Substitution Test/Coding (DSST, (14)). The lower the score, the stronger the indication of fatigability
Self-rated post-concussion symptoms	
	For assessment of self-rated symptoms The Rivermead Post-Concussion Symptoms Questionnaire (RPQ, (15)) was used. RPQ is based on a Likert scale and includes 16 items with ratings from 0 to 4. Higher score indicates more symptoms.
Secondary outcome measures	
Trait fatigability	The Fatigue Severity Scale (FSS (16)) was used to measure trait fatigue. FSS consists of 9 questions and is based on a 7 point Likert scale A high score implies a higher level of fatigue.

Anxiety and depression	Hospital Anxiety and Depression (HADS, (17)) scale was used to screen for depression and anxiety, higher scores indicate more severe problems
Self-rated visual symptoms in near work	Convergence Insufficiency Symptom Survey (CISS, (18)) was used to assess near work-related visual symptoms. Total score is 60 and a value above 21 indicates a high level of symptoms.
Visual disturbances	A visual examination performed by a licensed optometrist, using standard optometric clinical methods. Diagnosis of visual dysfunction were based on established diagnostic criteria (19).

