#### STATISTICAL ANALYSIS

Descriptive statistics will be used to depict demographics, injury characteristics, results on neuropsychological tests and psychological screening instruments. Multi-subject and multi-session analysis based on general linear model will be performed and assessed using statistical tools including regression analysis and 2-way ANOVA.

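### Does the plan leave open whether the visual outcomes are analysed as measurements or as yes/no diagnoses?

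*Combined protocol and SAP*

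**What the plan says.** Under Outcome variables, Table 1 has a secondary-outcome row for visual disturbances. It names an examination by a licensed optometrist and adds: "Diagnosis of visual dysfunction were based on established diagnostic criteria (19"). CISS has its own row, which states: "Total score is 60 and a value above 21 indicates a high level of symptoms".

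The Self-assessment part of Measures covers the same ground twice.

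- One paragraph lists the tests: "Included in the assessment was tests of visual acuity, refractive error, stereoacuity, accommodation, heterophoria, eye motility and fusional vergence". Convergence is not in this list. For CISS it says: "Total score is 60 and the cut-off score for abnormally high levels of symptoms is 21".
- The later paragraph also opens with the diagnosis. It then lists the visual functions measured, ending with "near point of accommodation, and near point of convergence", and restricts the analysis: "Only convergence, accommodation, fusional vergence, and CISS will be analyzed in this project". It says openly that the choice rests on earlier findings in the same data and on clinical experience.

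Statistical analysis gives the methods in general terms: "Multi-subject and multi-session analysis based on general linear model will be performed", with regression and 2-way ANOVA as tools. No method is tied to a particular visual variable.

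**The concern.** Table 1 can be read as making a diagnosis the outcome, and the later restriction as making three functions and a questionnaire the outcome. These would be different variables, and the form of each is not written down. CISS raises the same question, since both a total out of 60 and a cut-off are given. The cut-off itself is worded in two ways, which leaves a score of exactly 21 unclear.

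Two things would be at stake. The first is information: in a very small sample, replacing a measurement by yes/no can hide an association with connectivity. The second is analyst freedom: the data are already collected and partly reported, so an unspecified form could in principle be picked after seeing which version gives a result.

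**Working it through.** **No planned figure to reproduce.** The only power statement (Sample size: 12 per group, 80% power, alpha 0.05) concerns voxel-level activation. It gives no effect size or SD, so it cannot be rebuilt, and it does not address the visual outcomes.

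**Which form does the text point to?**

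| Place | Content | Points to |
|---|---|---|
| Table 1, visual row | Optometric examination; basis on which diagnoses were made | Neither form is named as the tested endpoint |
| Self-assessment, later paragraph | Functions measured, including two near points; then the restriction | Measured values |
| Statistical analysis | General linear model, regression, 2-way ANOVA | Measured values; regression could include a logistic model, but none is named |
| Table 1 and Self-assessment, CISS | Total out of 60, plus a cut-off | Score for analysis, cut-off for interpretation |

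The restriction lists functions, not diagnoses. Taken with the named methods, the ordinary reading is measured values, with diagnoses left to description.

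**What a yes/no analysis would cost, if one were done.** Participants at follow-up: (15 − 2) + (15 − 2) = 26, from Patient characteristics and the section on recruitment and non-participants. The dysfunction rate p is not in the documents, so 10% to 50% is assumed. For a normal variable cut once, the information kept about a correlation is φ(z)² / [p(1 − p)], where z is the normal quantile for p.

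| p | Information kept | Equivalent participants (× 26) |
|---|---|---|
| 10% | 0.342 | 8.9 |
| 20% | 0.490 | 12.7 |
| 30% | 0.576 | 15.0 |
| 50% | 0.637 | 16.6 |

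The loss is therefore 36% to 66%. More than half the information survives at rates of 30% and 50%.

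**Power for an association.** Assume one connectivity score, bivariate normality and a two-sided correlation test (40,000 simulations per figure). The yes/no range runs over p = 10% to 50%.

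| n, true correlation | Measured, 0.05 | Measured, 0.05/3 | Yes/no, 0.05 |
|---|---|---|---|
| 26, 0.5 | about 77% | 61% | 29–55% |
| 26, 0.4 | 54% | about 37% | 20–37% |
| 26, 0.3 | 32% | 18% | 13–22% |
| 13 (mTBI only), 0.5 | 43% | 26% | 14–28% |

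A single measured test beats a single yes/no test in every row. Measuring three functions means three tests, however. After correction the advantage is clear only in the first row.

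**Power for a group difference.** With 13 per group and two-sided alpha 0.05, the noncentral t (24 degrees of freedom, noncentrality d√(13/2)) gives 80% power at d ≈ 1.15. Cutting the same shift at an assumed control rate p gives an mTBI rate q = Φ(Φ⁻¹(p) + d). For p = 20%, q = 62% and Fisher power is 51%. Over p = 5% to 50%, Fisher power is 22% to 54%.

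**How far this depends on the diagnosis being one cut on one function.** Suppose instead that it is a cut on the sum of three functions, each correlated 0.5 with connectivity and with one another. Power with n = 26 is then 43%, 61%, 71% or 77% at p = 10%, 20%, 30% or 50%, against 61% for each corrected measured test (86% that at least one of the three is significant). The per-test ranking can reverse.

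**The case for a change.** The strongest case for a change is that Table 1 is the formal outcome list, it mentions diagnosis and no measured variable, and no sentence settles the form. One line would settle it at no cost, and the case for fixing an endpoint in advance does not depend on any power figure. The per-test advantage of measured values also holds throughout when no correction is made.

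It stands that the form is unstated and that one line would make Table 1 and the Self-assessment section read alike. It does not stand that the two places conflict. The Table 1 row describes an examination and the basis for diagnoses, and the later text narrows that row to named functions. Nor does it stand that the omission largely decides what can be detected. Even with measured values, 13 per group gives 80% power only for differences of about 1.15 SD, so sample size is the main limit whichever form is used.

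The link to the aim is also looser than it first appears. The objective asks "how this is related to symptoms and symptom resolution". Optometric findings are signs; CISS is the visual symptom measure, and its total is available. A score of exactly 21 is immaterial when the total is analysed. Convergence, missing from one list, is supplied by the next.

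**Conclusion.** This is missing detail that an analyst would fill sensibly from the plan itself. The measured functions, the near points and the linear-model methods all lead to analysing measured values and the CISS total, with diagnoses and the cut-off used descriptively. Writing that down would be harmless tidying and would probably change no result.

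The possible loss is real but conditional: 36% to 66% of the information, under a single cut on a normal variable at assumed rates of 50% down to 10%, and only if a yes/no analysis replaced the measurements. The power comparisons rest further on an assumed correlation and a single connectivity score. The documents give neither, and the section on resting-state fMRI data processing plans ICA, dual regression and permutation testing instead. These outcomes are secondary, and no change to the plan follows.

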#### *NEUROPSYCHOLOGICAL ASSESSMENT*

The Digit Symbol Substitution Test/Coding (DSST, (14)) from the Wechsler scales, is primarily used for measuring psychomotor processing speed. The task is ongoing for 120 s during which the participant is expected to fill in symbols paired to digits. The score is the number of symbols correctly completed, higher score indicates better result. In this study DSST was used to measure Fatigability (DSST-f). DSST-f was calculated by subtracting the score for the first half of the test (60 first seconds) from the last part of the test (60 last seconds). A negative score implies a slower performance during the latter part of the test, which is indicative of fatigability(23). DSST-f has previously been demonstrated to be a sensitive measure for fatigability, but not depression, in patients with mTBI (24).

The Swedish Lexical Decision Test was used at to assess premorbid IQ. The Swedish Lexical Decision test measures the premorbid estimated full-scale intelligence quotient (IQ), based on that word knowledge and cognitive functioning generally are associated, and that this association are relatively unaffected by TBI (25). In this test, the subject must make a lexical decision by judging if target words are real or fictitious. The Swedish Lexical

Decision Test has been demonstrated to explain 48 % of the variance of full-scale IQ from the WAIS-R and 31 % of demographic variables alone (25). If used in combination with demographic variables the estimation of premorbid cognitive functioning is further improved (25).

#### DATA MANAGEMENT

All data material are recorded with a participant ID and will be unidentifiable. Only [name] and [name] have access to the list that link participant ID with names. De-identified data will be electronically stored on the server at Danderyd University Hospital and will be deleted 10 years after the project has ended. The final dataset will be available to researchers actively contributing to statistical analyses and publications. Data entry will be controlled by initial exploratory analyses, including range checks, in order to promote data quality.

#### CONFIDENTIALITY

Information on participants will be handled by health care professionals adhering to Swedish Law ensuring confidentiality and data protection. Results and data will be presented at a group level in publications, rendering identification of individual patients impossible. All data will be stored in accordance with the General Data Protection Regulation (GDPR).

#### STATISTICAL ANALYSIS

Descriptive statistics will be used to depict demographics, injury characteristics, results on neuropsychological tests and psychological screening instruments. Multi-subject and multi-session analysis based on general linear model will be performed and assessed using statistical tools including regression analysis and 2-way ANOVA.

#### *PLANS FOR COMMUNICATING IMPORTANT PROTOCOL AMENDMENTS TO RELEVANT PARTIES*

Important protocol modifications will be reported to the Ethics committee in Sweden and amendments will be made to the trial registry (Clinicaltrials.gov).

#### *DISSEMINATION PLANS*

Publications are planned for journals in the fields of neuropsychology, and rehabilitation. Results will further be spread at relevant conferences, national and international meetings, and expert forums. The results will be shared with user organizations and its members as well as relevant policy makers.

#### ETHICS

Ethics approval was obtained from the Regional ethical review board in Stockholm, diary no: 2014/597-31/1. The study adhered to the tenets of the Declaration of Helsinki.

